8.6 Expedited Reporting

The Sponsor/designee will report all relevant information about Suspected Unexpected Serious Adverse Reactions (SUSARs) that are fatal or life-threatening as soon as possible to EudraVigilance for applicable European competent authorities, other regulatory authorities, as applicable, and to applicable Ethics Committee(s), and in any case no later than 7 days after knowledge by the Sponsor/designee of such a case. Relevant follow-up information will subsequently be communicated within an additional 8 days.

All other SUSARs will be reported, as applicable, to EudraVigilance for applicable European competent authorities, other regulatory authorities, as applicable, and to applicable Ethics Committee(s) as soon as possible but within a maximum of 15 days of first knowledge by the Sponsor/designee.

The Sponsor/designee will also submit any additional expedited safety reports required in accordance with the timelines outlined in country-specific legislation.

The Sponsor/designee will also inform all Investigators as required per local regulation.

The requirements above refer to the requirements relating to IMPs.

8.7 Special Situation Reports

Special Situation Reports include reports of IMP overdose, misuse, abuse, medication error, and reports of adverse reactions associated with product complaints.

- **Overdose:** Refers to the administration of a quantity of a medicinal product given per administration or cumulatively (accidentally or intentionally), which is above the maximum recommended dose according to the Protocol. For this study, a single intake of 5 or more setanaxib tablets and/or a total daily dose of 7 or more tablets will be considered an overdose. Clinical judgment should always be applied. In cases of a discrepancy in the drug accountability, overdose will be established only when it is clear that the patient has taken additional dose(s), or the Investigator has reason to suspect that the patient has taken additional dose(s).
- **Misuse:** Refers to situations where the medicinal product is intentionally and inappropriately used in a way that is not in accordance with the Protocol instructions or local prescribing information and may be accompanied by harmful physical and/or psychological effects.
- **Abuse:** Is defined as persistent or sporadic, intentional excessive use of a medicinal product, which is accompanied by harmful physical or psychological effects.
- **Medication error:** Is any unintentional error in the prescribing, dispensing, or administration of a medicinal product by a healthcare professional, patient, or consumer. The administration or consumption of the unassigned treatment and administration of an expired product are

always reportable as medication errors; cases of patients missing doses of investigational product are not considered reportable as medication errors.

All special situation events as described above must be reported on the Special Situation Report form and emailed to the Calliditas Patient Safety Mailbox (contact information listed in [Section 8.3.1](#)) within 24 hours of knowledge of the event. All AEs associated with these Special Situation Reports should be reported as AEs or SAEs as well as recorded on the AE eCRF and reported to the Calliditas Patient Safety Mailbox by completing the Safety Report Form. Details of the symptoms and signs, clinical management, and outcome should be provided, when available.

8.8 Clinical Laboratory Evaluations

Clinical laboratory evaluations (including serum chemistry, hematology, endocrinology, and urinalysis) will be collected at timepoints specified in [Appendix A](#).

Baseline values for liver tests (ALT, AST, and total bilirubin) are determined by averaging the values obtained at Screening Visits 1 and 2 to obtain the arithmetic mean.

For WOCBP only: a serum pregnancy test will be performed at Study Visit 2. A pregnancy test via a local urine assessment will be performed at all other applicable study visits prior to study drug dosing.

The total number of venipunctures and the total volume of blood collected during the study will be limited to that needed for PK, PD, and safety assessments. The total whole blood volume collected during the study will not exceed those allowed per European Medicines Agency guidance (Ethical considerations for clinical trials on medicinal products conducted with minors).

See [Appendix B](#) for the complete list of analytes.

8.8.1 Detection and Management of Potential Bone Marrow Toxicity

Particular attention will be given to the detection and management of potential cases of bone marrow toxicity. In case of Grade ≥ 2 severity anemia, the Investigator will instruct the patient to interrupt IMP administration and to return to the study site within 7 days so that the absolute reticulocyte count can be retested. If the retest value is below 50% of the baseline value (Screening Study Visit 2), IMP will not be resumed and will be permanently discontinued. IMP administration will be resumed only if the retest value of the absolute reticulocyte count is $\geq 50\%$ of the baseline value and a Grade ≤ 1 of anemia, and an alternative cause for the anemia can be documented. The patient will continue to be closely monitored (at least weekly) until normalization of the reticulocyte count, ie, return to baseline values.

Anemia will be reported to the Sponsor (or designee) as an AESI, as defined in [Section 8.1.4](#), following the same procedure as for SAEs ([Section 8.3](#)).

8.8.2 Suspected Drug-Induced Liver Injury

During the study, the Investigator will remain vigilant for increases in liver enzymes and other measures of liver function. In the event that the patient has any of the following laboratory results, the Investigator should refer to [Appendix C](#) for details regarding the detection and management of suspected DILI, including instructions for retesting, close monitoring, and action to take regarding the IMP:

- AST or ALT $\geq 3 \times$ ULN;
- AST or ALT $>2 \times$ Baseline; or
- Total bilirubin $>2 \times$ ULN.

If there is a reported case of suspected DILI, an ad-hoc IDMC meeting will be scheduled for an unblinded review of safety data. The study enrollment will be paused awaiting IDMC review and recommendation. IMP treatment of already enrolled study patients may continue pending IDMC recommendation.

8.9 Vital Signs

Vital signs will be collected at timepoints specified in [Appendix A](#), including at Screening, Day 1 (pre-dose and 3 and 6 hours post-dose), Weeks 2, 6, 12, and 18 (pre-dose), Week 24 (pre-dose and 3 and 6 hours post-dose), and at the Follow-up Visit. Timing windows for vital signs measurements are ± 10 minutes for 3 hours post-dose and ± 20 minutes for 6 hours post-dose.

Vital sign measurements will include systolic and diastolic blood pressure and heart rate. Blood pressure and heart rate will be measured after resting in the supine position for at least 5 minutes and will be measured 3 times with each measurement separated by at least 1 minute (the lowest value will be recorded on the eCRF).

8.10 Electrocardiograms

12-lead ECGs will be collected at timepoints specified in [Appendix A](#), including at Screening, Day 1 (pre-dose and 3 and 6 hours post-dose), Weeks 2, 6, 12, and 18 (pre-dose), Week 24 (pre-dose and 3 and 6 hours post-dose), and at the Follow-up Visit. Timing windows for ECGs are ± 10 minutes for 3 hours post-dose and ± 20 minutes for 6 hours post-dose.

ECGs should be collected in triplicate, 1 to 3 minutes apart, and read locally. Investigators and site staff are encouraged to consult with a local cardiologist, if needed, to interpret suspected QT prolongation or other clinically significant abnormalities.

If collected at the same time point as PK blood draws, ECGs should be recorded before blood draws to avoid effects of blood draw on autonomic tone.

8.11 Physical Examinations

Physical examinations will be performed at timepoints specified in [Appendix A](#).

Physical examinations will include the following body systems: general appearance, skin, head, ears, eyes, nose, throat, neck, lungs, heart, abdomen, musculoskeletal, extremities, and neurological systems.

8.12 Weight and Height

Height and weight will be collected at all timepoints specified in [Appendix A](#).

Height will be collected at the beginning (Study Visit 3/Day 1) and at the end of the study (Study Visit 8/Week 24) and, for patients between 12 and 17 years of age, at all other visits where eGFR is calculated. Weight will be collected for all patients at all timepoints.

8.13 Hearing Examinations

Hearing examinations will be completed at timepoints specified in Appendix A.

Pure tone audiometry (PTA) air conduction thresholds will be conducted at frequencies 250, 500, 1000, 2000, 4000, and 8000 Hz.

PTA bone conduction thresholds will be conducted at frequencies 500, 1000, 2000, and 4000 Hz.

9 STATISTICS

9.1 Analysis Sets

The following analysis sets will be defined in the study:

- The Full Analysis Set (FAS) will be defined as all randomized patients;
- The Safety Analysis Set (SAS) will be defined as all randomized patients who take at least 1 dose of the study drug; and
- The PK Analysis Set will be defined as all randomized patients who take at least 1 dose of the study drug and have sufficient setanaxib plasma concentration data to calculate at least 1 PK parameter.

Other analysis sets may be defined as appropriate and, if applicable, will be described in the Statistical Analysis Plan (SAP).

9.2 Statistical Methods

Details of the statistical analyses, including supportive and sensitivity analysis if needed, will be provided in the SAP, which will be finalized prior to database lock and unblinding.

All endpoints will be summarized descriptively, and no formal hypothesis testing will be conducted. Descriptive statistics for continuous variables will include number of patients (n), mean, standard deviation, median, minimum, and maximum values. Analysis of categorical variables will include counts and percentages. Any statistical modeling or comparison, along with any associated p-values, will be considered nominal.

9.2.1 Analysis of Safety

To assess the primary objective, the primary safety estimand for SAE is defined by the following key attributes, according to the framework provided in International Council for Harmonisation (ICH) E9 (R1):

Treatment: Setanaxib treated patients compared to placebo.

Population: The SAS comprised of all randomized patients who took at least 1 dose of the study drug.

Variable of interest: SAEs.

Intercurrent event handling: All events will be counted regardless of early discontinuation of treatment, up to 30 days post-last dose of study drug.

Summary measure: Count and percentage of patients experiencing SAEs during the Treatment Period up to 30 days post-final dose.

The analysis of the primary endpoint will be performed using the SAS. The number and percentages of patients with SAEs and treatment-emergent AESIs will be presented by treatment group, system organ class, and preferred term. Additional summaries of AEs, TEAEs, AEs leading to discontinuation of study treatment, and AEs by severity, seriousness, and relationship to study drug(s) will be presented.

Clinical laboratory parameters, vital signs, ECGs, thyroid, hearing and physical examinations will be summarized by treatment group by visit. Change from baseline values by visit will be presented for the continuous parameters. The count (and percentage) of patients with clinically significant changes will be tabulated by treatment group.

9.2.2 Analysis of Efficacy

The analysis of secondary and exploratory endpoints will be performed using the FAS.

The UPCR data will be log-transformed prior to analysis. The analysis of the ratio of UPCR at 24 weeks compared to baseline will be analyzed using a mixed model repeated measurement approach. The analysis will include fixed effects for treatment, visit, and treatment by visit interaction, along with the log-transformed baseline value as a covariate. Model assumptions will be checked and, if not met, appropriate data transformations may be applied, or non-parametric approaches will be considered.

The proportions of patients achieving a 25% reduction in UPCR at 24 weeks from baseline in the setanaxib group will be compared to placebo group using a chi-square test.

The eGFR data will be log-transformed prior to analysis. eGFR data are such that it is possible there will be a small number of patients with extreme outlying data. Therefore, the analysis of the ratio of eGFR at 24 weeks compared to baseline will be based on a Robust Regression. In order to handle missing data, the analysis will be performed over 3 phases: an imputation, analysis, and pooling phase. Further details will be provided in the SAP. Results of the ratio at 24 weeks compared to baseline will be back-transformed to obtain estimated mean changes from baseline.

Baseline UPCR and eGFR will be defined as the geometric mean of 2 assessments prior to randomization. Similarly, the 24-week UPCR and eGFR will be calculated as for baseline. More details will be provided in the SAP.

PK parameters will be estimated for each individual patient using non-linear mixed effect methodology and prior PK knowledge of the compound. Further details will be provided in the SAP. The following PK parameters will be determined:

- $AUC_{0-24-ss}$: Area under the concentration-time curve over 24 hours at steady state;
- C_{min-ss} : Minimum plasma concentration at steady state; and
- C_{max-ss} : Maximum plasma concentration at steady state.

Plasma concentration time data and plasma PK parameter data for setanaxib and GKT138184 will be presented using descriptive summaries.

The exploratory endpoints will be summarized descriptively by treatment group.

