2 STUDY OBJECTIVES AND ENDPOINTS

The objectives and endpoints of this study are provided in Table 1.

Table 1. Objectives and Endpoints

Primary Objective	Primary Endpoints
To evaluate the safety and tolerability of setanaxib compared to placebo in patients with Alport syndrome.	
 Percentage of patients with SAEs; and Percentage of patients with treatment-emergent AESIs, ie, anemia.
Safety Objectives	Safety Endpoints
To assess the effect of setanaxib on vital signs compared to placebo.	Percentage of patients with clinically significant changes in heart rate and blood pressure.
To evaluate the effect of setanaxib on 12-lead ECGs compared to placebo.	Percentage of patients with clinically significant changes in 12-lead ECG.
To evaluate the effect of setanaxib on physical examinations compared to placebo.	Percentage of patients with clinically significant changes in physical examination.
To evaluate the effect of setanaxib on clinical laboratory parameters compared to placebo.	Percentage of patients with clinically significant changes in hematology, serum chemistry, urinalysis, and thyroid function.
To evaluate the effect of setanaxib on hearing compared to placebo.	Percentage of patients with clinically significant changes in hearing audiometric testing (bone- and air-conduction).
Secondary Objectives	Secondary Endpoints
To assess the effect of setanaxib on UPCR compared to placebo.	
 The ratio of UPCR at 24 weeks compared to baseline; and Percentage of patients with a 25% reduction in UPCR at 24 weeks, compared to baseline.
To assess the effect of setanaxib on eGFR compared to placebo.	The ratio of eGFR at 24 weeks compared to baseline.
To assess the plasma exposure of setanaxib and its active metabolite GKT138184.	
Pre-dose and post-dose plasma concentrations of setanaxib and GKT138184 at steady state. The following PK properties will be calculated:
 
 Area under the concentration-time curve over 24 hours at steady state ($AUC_{0-24-ss}$); Minimum plasma concentration at steady state (C_{min-ss}); and Maximum plasma concentration at steady state (C_{max-ss}).
Exploratory Objectives	Exploratory Endpoints

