3.1 Summary of Study Design

This is a randomized, double-blind, placebo-controlled Phase 2a study assessing oral setanaxib in patients with Alport syndrome. The safety, tolerability, PK, PD, and preliminary efficacy of setanaxib will be assessed over 24 weeks of treatment. The study design is outlined in [Figure 1](#). The inclusion and exclusion criteria are designed to enroll a population of patients with Alport syndrome at risk of disease progression. In the EU, only adult patients (aged 18 to 50 years, inclusive) will be enrolled. Patients are required to have persistent proteinuria (UPCR ≥ 90 mg/mmol [0.8 g/g]) despite treatment with a stable dose of RAS inhibitor therapy (ACEis and/or angiotensin II type I receptor blocker [ARBs]) at the maximum allowed dose or maximum-tolerated daily dose for at least 8 weeks prior to consent/assent. A stable dose is defined as a dose within 25% of the dose at randomization. Patients should remain on their regimens of RAS inhibitors for the whole duration of the study. Patients with proven intolerance to ACEi and ARB are allowed in the study. This study aims to assess the safety of setanaxib as an add-on treatment to current RAS inhibitor treatment, in patients with Alport syndrome at risk of disease progression and with limited treatment options available. The double-blind, placebo-controlled design is chosen to provide safety data and preliminary efficacy for setanaxib in addition to the standard of care treatment in this patient population with a standard of care (with placebo) arm as reference. This will help to guide the design of further Phase 2/3 studies of setanaxib in Alport syndrome.

Patients must have UPCR ≥ 90 mg/mmol [0.8 g/g] at 2 consecutive measurements during Screening, separated by at least 2 weeks and calculated by the central laboratory. The baseline measurement will be the geometric mean of these 2 measurements. Patient must also have eGFR ≥ 30 mL/min/1.73 m² at Study Visit 1 or 2, calculated at the central laboratory using the Chronic Kidney Disease Epidemiology Collaboration formula (CKD-EPI) for patients ≥ 18 years of age and the revised bedside Schwartz formula for patients 12 to 17 years of age.

Eligible patients will be randomized in a 2:1 ratio to receive either setanaxib or placebo for 24 weeks, in addition to their stable dose of RAS inhibitor therapy, with setanaxib dosing based on age. In the EU, the setanaxib dose will be 1600 mg/day, as only adult patients will be enrolled.

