3.1.6 Hypothesis Testing

No formal hypothesis testing will be conducted.

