3.5.1 Urine Protein to Creatinine Ratio (UPCR)

The ratio of UPCR at 24 weeks compared to baseline will be analyzed using a mixed model repeated measurement (MMRM) approach and incorporate UPCR data from 6 weeks, 12 weeks and 24 weeks. Baseline and 24 weeks UPCR will be calculated as the geometric mean of 2 assessments and log-transformed prior to inclusion in the analysis model. The model will include fixed effects for treatment, visit, and treatment by visit interaction, along with the log-transformed baseline value as a covariate. Patient will be included as a random effect. An unstructured covariance matrix will be used to model the within patient correlation of data. If the model does not converge, other covariance structures may be considered. The Kenward-Roger approximation to estimate the degrees of freedom will be used. Model assumptions will be assessed using residual plots (such as q-q plots, histograms) and, if not met, other data transformations or non-parametric approaches may be considered. The LS mean and 2-sided 95% confidence intervals will be estimated.

The analysis will be implemented using SAS® Proc Mixed. Sample SAS code below:

```
*****
** TRT          = treatment group
** VISIT        = Visit name
** USUBJID      = Patient ID
** CHG_UPCR     = Change of log-UPCR at each visit from baseline
** BASE        = log-baseline UPCR
```

```
*****  
proc mixed data=data;  
  class TRT USUBJID VISIT;  
  model CHG_UPCR = TRT VISIT BASE TRT*VISIT/ddfm=kr;  
  repeated VISIT/ sub = USUBJID type = un;  
  estimate 'Week 24 effect' TRT -1 1;  
  lsmeans TRT*VISIT/cl pdiff;  
run;
```

The proportions of patients achieving a 25% reduction in UPCR at 24 weeks from baseline in the setanaxib group will be compared to placebo group using a Fischer's exact test.

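### UPCR responder endpoint: percentages per arm and a nominal p-value are planned, but no between-arm difference with a confidence interval

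*Protocol*

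**What the plan says.** Protocol Section 2 lists as a secondary endpoint the "Percentage of patients with a 25% reduction in UPCR at 24 weeks, compared to baseline". Protocol 9.2.2 says the responder proportions "in the setanaxib group will be compared to placebo group using a chi-square test". SAP 3.5.1 says they "will be compared to placebo group using a Fischer's exact test" (spelling as printed). Neither passage names a risk difference, risk ratio, odds ratio or confidence interval.

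The one interval statement in SAP 3.5.1, "The LS mean and 2-sided 95% confidence intervals will be estimated", closes the paragraph on the mixed model for the continuous UPCR ratio. It precedes the sentence on responders and does not cover it.

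The general rules add counts and percentages for categorical variables (Protocol 9.2, SAP 3.1.5). On testing, Protocol 9.2 states "All endpoints will be summarized descriptively, and no formal hypothesis testing will be conducted" and adds that any comparison and its p-value are to be regarded as nominal. SAP 3.1.6 says "No formal hypothesis testing will be conducted" and does not repeat the nominal label.

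On the use of the results, Protocol 3.1 says of the placebo-controlled design: "This will help to guide the design of further Phase 2/3 studies of setanaxib in Alport syndrome".

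**The concern.** A later trial is designed on an effect size and its uncertainty. For this endpoint the only between-arm output that the plan specifies is a p-value, which gives neither. With so few patients the p-value is driven largely by the sample size. A large observed benefit can look like a negative result, and p = 1.00 can be read as no effect when the data fit a large benefit or a large harm equally well. If no interval method is named in advance, anyone who wants one must choose it after unblinding, when the choice can change the impression given.

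**Working it through.** **Inputs.** The sample size is about 18, with a maximum of 20 (Protocol 9.2.3), allocated 2:1 (Protocol 3.1). Neither document states the split. It follows as 18 × 2/3 = 12 and 18 × 1/3 = 6; at 20 it is about 13 v 7. Missing responder data are not imputed (SAP 3.1.8), so the analysed numbers may be smaller. The size was chosen empirically, with no alpha, power or response rate stated, so there is no planned figure to reproduce. The counts below are illustrations.

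**Formulas.** For each arm, the Wilson limits (l, u) are [p + z²/2n ± z√(p(1−p)/n + z²/4n²)] / (1 + z²/n), with z = 1.96. The Newcombe interval for d = p1 − p2 runs from d − √[(p1−l1)² + (u2−p2)²] to d + √[(u1−p1)² + (p2−l2)²]. The two-sided Fisher p-value sums the hypergeometric probabilities of all tables, with margins fixed, that are no more probable than the one observed.

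**7/12 v 1/6.**
- p1 = 0.583 (0.320 to 0.807); p2 = 0.167 (0.030 to 0.564); d = 0.417.
- Lower limit: 0.417 − √(0.264² + 0.397²) = −0.060.
- Upper limit: 0.417 + √(0.223² + 0.137²) = 0.679.
- Fisher, with 8 responders in 18: the probabilities of 2, 3, 7 and 8 responders on setanaxib sum to 0.0015 + 0.0302 + 0.1086 + 0.0113 = 0.152.

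**3/12 v 1/6.**
- p1 = 0.250 (0.089 to 0.532); d = 0.083.
- Lower limit: 0.083 − √(0.161² + 0.397²) = −0.345.
- Upper limit: 0.083 + √(0.282² + 0.137²) = 0.397.
- Fisher p = 1.00.

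**More outcomes at 12 v 6** (differences in percentage points; chi-square uncorrected):

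| Setanaxib | Placebo | Difference | Newcombe 95% CI | Fisher p | Chi-square p |
|---|---|---|---|---|---|
| 7/12 | 1/6 | +42 | −6 to +68 | 0.15 | 0.094 |
| 3/12 | 1/6 | +8 | −34 to +40 | 1.00 | 0.69 |
| 4/12 | 0/6 | +33 | −10 to +61 | 0.245 | 0.11 |
| 11/12 | 4/6 | +25 | −11 to +62 | 0.245 | 0.18 |
| 6/12 | 3/6 | 0 | −40 to +40 | 1.00 | 1.00 |
| 8/12 | 1/6 | +50 | +2 to +74 | 0.13 | 0.046 |
| 11/12 | 3/6 | +42 | +0.3 to +74 | 0.083 | 0.045 |

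Rows 3 and 4 share one Fisher p-value but have different estimates. Rows 2 and 5 both give p = 1.00, with intervals reaching 40 points of benefit and at least 34 points of harm. Over all 13 × 7 = 91 possible outcomes, the Newcombe width runs from 46 to 80 points.

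**Dependence on test and split.** By Fisher, the smallest benefit giving p < 0.05 is 50 points at 12 v 6 (12/12 v 3/6, p = 0.025), 43 points at 13 v 7 (13/13 v 4/7, p = 0.031) and 60 points at 11 v 5. Under the Protocol's chi-square test without correction, the last row of the table already reaches p = 0.045 at +42 points. No single threshold describes the plan.

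**Agreement of interval and p-value.** At 12 v 6 there are 20 outcomes with a benefit of at least 40 points. Seven have Fisher p ≥ 0.05, and in four of those seven the Newcombe interval excludes zero: 6/12 v 0/6, 8/12 v 1/6, 10/12 v 2/6 and 11/12 v 3/6.

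**The case against.** The other side has a good case on four counts.

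- **No contradiction over testing.** A reader might infer that a test has no place in a trial that disclaims formal hypothesis testing. The documents do not support that: Protocol 9.2 expects p-values and limits them to nominal status. That the SAP omits the label is a matter of emphasis.
- **Effect size is not absent.** A reader might also infer that the response rates go unreported. Counts and percentages per arm are planned, so the point difference is one subtraction, and an interval could be calculated from the four counts. What is missing is a planned estimate with an interval by a method fixed in advance.
- **UPCR has an interval elsewhere.** The mixed model gives least-squares means with 95% intervals, and its sample code requests confidence limits and pairwise differences. That analysis uses the measurement that the responder endpoint dichotomises, so later design need not rest on the responder rate alone.
- **An interval can conflict with Fisher.** It can, as the working shows. This is a reason to say in advance which result leads, not a reason to omit the interval.

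Low power is no criticism either, since the trial was sized empirically and claims none. All four points stand, and they narrow the matter to one unplanned interval on a secondary endpoint.

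**Conclusion.** The gap is real and modest. For the responder endpoint the plan provides percentages per arm and a nominal p-value, but no between-arm estimate with an interval. At about 12 v 6 the p-value is a poor guide to effect size: +42 points gives p = 0.15, and p = 1.00 is compatible with differences from −34 to +40 points. No analysis is invalid, the primary safety analysis is untouched, and no decision rule in the documents depends on this p-value.

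The figures assume the derived 12 v 6 split, complete responder data, Fisher's test and Newcombe intervals. A reader might infer that no benefit below 50 points can reach p < 0.05; that holds only for Fisher at exactly 12 v 6. The conclusion that an interval should be planned does not depend on the test or the split.

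**What to change.** In SAP 3.5.1, replace the responder sentence along these lines:

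*The proportion of patients with at least a 25% reduction in UPCR at Week 24 will be presented by treatment group, with the difference (setanaxib minus placebo) and its 95% confidence interval by [one named small-sample method, e.g. Newcombe or Miettinen-Nurminen]. The interval is the main result and is descriptive, not a significance test. Any Fisher's exact p-value is nominal and supportive.*

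Choose the method before unblinding. Carry the same text into Protocol 9.2.2 at the next amendment; this point alone does not justify an amendment. Until then, record the departure in SAP Section 6. That section lists two changes from the Protocol, and the move from chi-square to Fisher is not one of them, so the entry is needed anyway.

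The cost is one SAP sentence, one line in Section 6 and one table row, with no new data. The downside is that the table will show how wide the uncertainty is, and that interval and p-value will sometimes disagree (8/12 v 1/6: +2 to +74, p = 0.13). The text therefore has to state that the interval leads.
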